6.0 STATISTICAL CONSIDERATIONS

A) Assumptions.

Single-procedure versus multiple-procedure success. Our initial preliminary data suggested an overall procedure success of 45% in patients undergoing PVAI and 61% for those undergoing VOM-PV (difference of 16%). This included patients with repeat procedures performed in some, but not all of the failed procedures (45% all patients in the PVAI group and 30% in the VOM-PV group). **The single-procedure success was 38% in patients undergoing PVAI and 56% in patients undergoing VOM-PV** (difference of 18%). Thus, the endpoint of single-procedure success is likely to show greater differences amongst groups.

Mortality. The expected mortality is low in this study as it has been in AF ablation trials.

Mortality will be recorded as a safety endpoint.

One-year follow-up time. In previous versions of the protocol, additional follow-up time (up to 15 months) was included in the VENUS trial, in order to accommodate for appropriate follow-up of patients undergoing repeat procedures. Therefore, a trial duration of 12 months is sufficient if just single-procedure success is the primary efficacy endpoint. Procedural failures (events counted as the primary efficacy endpoint) occur mostly during the first year. Additionally, 12-month follow-up is consistent with the recommendations for clinical trials in AF by the HRS/EHRA/ECAS Catheter and Surgical Ablation consensus document.²

Unknown classification as success or failure. Patients who cannot be classified as successes or failures on the primary efficacy endpoint will be excluded from the primary analysis.

B) VENUS Group Sequential Clinical Trial Design

Power and sample size determination. Group sequential two proportions power analysis using simulation was performed using PASS V12 (Kaysville, UT). The following assumptions were made:

- Response rate in PV-VOM: $p_1=0.56$
- Response rate in PVAI: $p_2= 0.38$
- Hypotheses: $H_0: p_1= p_2$; $H_1: p_1 \neq p_2$
- Test Statistic: Z-Test (Unpooled)
- Zero Adjustment Method: None
- Alpha-Spending Function: O'Brien-Fleming Analog
- Beta-Spending Function: None
- Futility Boundary Type: None
- Number of Looks: 3
- Simulations: 100000

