- Enrollment as AF or AT –for MARS-AF trial only.
- Pre-existing low voltage scar and extent of low-voltage scar after ablation procedure (divided in tertiles).

Primary Outcome. Hypothesis tests for the equality of two proportions (unpooled standard errors) will be employed for determining whether or not the VOM success rate is significantly greater than the success rate for PVAI. The test statistic is a z-score which is standard normal distributed and the relevant lookup critical values (percentage points) are listed in the interim analysis section for group sequential designs. From a post-hoc perspective, we may use the stratified Mantel-Haenszel odds ratio test of proportions if we learn that success rates track with a particular covariate, such as LA volume or AF duration, and the strata weights are not highly imbalanced.

Secondary Outcomes. The secondary outcomes are listed below along with their corresponding storage location (various tables or Excel .csv files on output after report generation). Model building strategies (MBS) will be employed using univariate and multivariable regression models for post-hoc analyses of secondary outcomes. During MBS, univariate predictors whose $p < 0.25$ will be selected as multiple variable model candidates. MBS regression methods may include linear, logistic, Poisson, and Cox proportional hazards (PH) along with regression diagnostics using the relevant goodness-of-fit criteria, residuals, variance inflation factors (VIF), ROC-AUC, and assumption-checking techniques (e.g. normally-distributed standardized residuals for linear regression). Regression diagnostics for linear regression will include estimation and filtering of overly influential records based on residuals, standardized residuals, deletion residuals, Cook's distance, leverage, DFFITS, DFBETAS, and VIFs. Regression diagnostics for logistic and Poisson regression will include filtering on Pearson, deviance, and leverage residuals and the Hosmer-Lemeshow test for logistic regression GOF. Cox PH regression diagnostics will include Schoenfeld and Nelson-Aelen residuals, and possible employment of stratified models when the PH assumption fails.

The table below lists the primary outcomes which are to be analyzed during each interim analysis, as well as the secondary outcomes which will be analyzed and reported prior to all DSMB review meetings.

Primary Endpoints	EDC Pages	Data Fields

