Missing data. The critical piece of data required for endpoint analysis is the electrocardiographic event monitor. Failure to comply with wearing the monitor will lead to missing data. We request patients to wear monitors for 1–month. However, only a minimum of 1-week of monitored time is required for Endpoint assessment. Patients with less than 1 –week of monitoring will be considered as missing data. Patients who die before then study end will be considered not to have a response to treatment. For patients with missing primary outcomes, we will perform multiple imputation (MI) based on Monte Carlo Markov chain (MCMC) methods (Refs 1-3). MI will only be used for dealing with missing data as a secondary analysis tool of the primary endpoint. In Stata, MI is available for many procedures, especially the regression modules (linear, logistic, Poisson, Cox PH). MI can be performed to iteratively impute central estimates of missing outcome measures based on subjects' covariate patterns. The most straightforward example can be envisioned in this study, where logistic regression with MI is employed to train a model based on primary outcome (0-failure,1-success) as the dependent variable and age, gender, baseline AF duration, and baseline LA volume as independent predictors to impute $P(y=1|x)$ for subjects with missing primary outcome.

Sensitivity analysis. Following methods introduced in Proschan et al. (Ref 4), we simulated success rates for patients with missing 12-month outcomes in VOM and PVAI arms for VENUS and MARS at 33%, 66%, and 100% information time (looks 1-3). $B=100,000$ iterations were used with proportions of $P_m=0, 0.05, 0.10, 0.15$, and 0.2 representing the amount of missing data in both VOM and PVAI arms. At look k , let the success rate in the VOM arm be p_{1k} and the success rate in the PVAI arm be p_{2k} , n_{1k} and n_{2k} the number of patients accrued in the VOM and PVAI arms, $n_{1k}^m = n_{1k}P_m$ and $n_{2k}^m = n_{2k}P_m$ the number of patients in VOM and PVAI arms with missing outcome data, and $n_{1k}^0 = n_{1k} - n_{1k}^m$ and $n_{2k}^0 = n_{2k} - n_{2k}^m$ the number of patients in VOM and PVAI arms without missing outcomes. Next, for VOM patients with missing

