outcomes, simulate the number of successes by taking random draws of a binomial variate with parameters (n_{1k}^m, p_2) , and the number of successes among PVAI patients with missing outcomes as $B(n_{2k}^m, p_1)$. Note that the random draws of binomial variates are based on the success rate in the opposing arm, which enforces a high level of conservatism. A test statistic (unpooled variance) at the b th iteration is

$$Z_k^{(b)} = \frac{\hat{p}_{1k} - \hat{p}_{2k}}{\sqrt{\frac{\hat{p}_{1k}(1-\hat{p}_{1k})}{n_{1k}} + \frac{\hat{p}_{2k}(1-\hat{p}_{2k})}{n_{2k}}}}$$

where $\hat{p}_{1k} = [n_{1k}^0 p_{1k} + B(n_{1k}^m, p_2)]/n_{1k}$ is the unobserved success rate among VOM patients with and without missing data, and $\hat{p}_{2k} = [n_{2k}^0 p_{2k} + B(n_{2k}^m, p_1)]/n_{2k}$. The power of the test is equal to the proportion of rejections among the B iterations, given in the form

$$Power = \frac{\#\{b: Z_k^{(b)} > 1.96\}}{B}.$$

The tables below present power as a function of VOM and PVAI success rates, and the proportion of patients with missing data for the VENUS and MARS trials.

VENUS 33%		PVAI Success					
		Missing	0.28	0.33	0.38	0.43	0.48
VOM Success 0.46	0	1.000	0.000	0.000	0.000	0.000	0.000
	0.05	0.778	0.055	0.000	0.000	0.000	0.000
	0.1	0.462	0.054	0.002	0.000	0.000	0.000
	0.15	0.247	0.051	0.003	0.000	0.000	0.000
	0.2	0.197	0.052	0.007	0.001	0.000	0.000
0.51	0	1.000	1.000	0.000	0.000	0.000	0.000
	0.05	1.000	0.584	0.059	0.000	0.000	0.000
	0.1	0.855	0.461	0.045	0.001	0.000	0.000
	0.15	0.601	0.213	0.043	0.002	0.000	0.000
	0.2	0.445	0.159	0.042	0.008	0.001	0.000
0.56	0	1.000	1.000	1.000	0.000	0.000	0.000
	0.05	1.000	1.000	0.476	0.060	0.000	0.000
	0.1	1.000	0.854	0.459	0.049	0.001	0.000
	0.15	0.907	0.514	0.218	0.040	0.003	0.000
	0.2	0.709	0.397	0.154	0.045	0.011	0.000
0.61	0	1.000	1.000	1.000	1.000	0.000	0.000
	0.05	1.000	1.000	1.000	0.477	0.058	0.000
	0.1	1.000	1.000	0.860	0.452	0.053	0.000
	0.15	0.990	0.879	0.510	0.227	0.034	0.000
	0.2	0.901	0.696	0.383	0.146	0.049	0.000
0.66	0	1.000	1.000	1.000	1.000	1.000	0.000
	0.05	1.000	1.000	1.000	1.000	0.478	0.000
	0.1	1.000	1.000	1.000	0.868	0.434	0.000

0.15	1.000	0.991	0.866	0.513	0.233
0.2	0.982	0.905	0.682	0.367	0.153

VENUS 66%
(n1=120,n2=104)

VOM Success	Missing	PVAI Success				
		0.28	0.33	0.38	0.43	0.48
0.46	0	1.000	1.000	0.000	0.000	0.000
	0.05	1.000	0.766	0.008	0.000	0.000
	0.1	0.976	0.473	0.024	0.000	0.000
	0.15	0.777	0.243	0.018	0.000	0.000
	0.2	0.532	0.159	0.020	0.001	0.000

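### The only imputation model the plan describes, an example, omits randomised arm; if used, it shrinks the treatment difference in the secondary analysis of the primary endpoint by about the missing fraction

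*Combined protocol and SAP*

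**What the plan says.** All of this is in section 6.0 of the combined protocol and SAP.

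- **Primary analysis.** Under Assumptions, patients who cannot be classified as success or failure "will be excluded from the primary analysis". Under Primary Outcome, "Hypothesis tests for the equality of two proportions (unpooled standard errors) will be employed". The primary result is therefore a complete-case comparison of two proportions.
- **Role of MI.** The Missing data paragraph commits to MI by Markov chain Monte Carlo methods, cites three references, names Stata, and adds: "MI will only be used for dealing with missing data as a secondary analysis tool of the primary endpoint".
- **What is imputed.** "MI can be performed to iteratively impute central estimates of missing outcome measures", based on the subjects' covariate patterns.
- **The model.** It is introduced with "The most straightforward example can be envisioned in this study": a logistic regression of success or failure that uses "age, gender, baseline AF duration, and baseline LA volume as independent predictors to impute" P(y=1|x).
- **Separate sensitivity analysis.** The plan simulates missing proportions of 0, 0.05, 0.10, 0.15 and 0.20, "representing the amount of missing data in both VOM and PVAI arms". It fills each arm at the other arm's success rate, a choice "which enforces a high level of conservatism".

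No part of the plan puts arm into the imputation model or imputes within arm. The logistic model under Use of propensity scores does involve arm, but as the outcome. It is not an imputation model.

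**The concern.** An imputation model should contain the variable whose effect the completed data will be used to estimate. Here that variable is randomised arm. Randomisation makes the baseline covariates independent of arm, so a model built only on them cannot tell the arms apart. It assigns missing VOM-PV and PVAI patients the same average success rate and pulls the two proportions together.

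MI is the named secondary analysis for the patients whom the primary analysis drops. If it differs from the primary result, a reader will suspect that missing data are driving that result. Without arm, such a gap would appear even under missingness completely at random, where the complete-case result is valid. The opposing-arm simulation also leans toward no difference, but the plan labels it conservative. The MI carries no such label.

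The text is also unclear on whether 0/1 outcomes are drawn or P(y=1|x) itself is filled in, and it does not say how results are pooled. Both affect the standard error.

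**Working it through.** **Inputs from section 6.0.** VENUS: 180 v 156 patients, success 0.56 v 0.38, final boundary 2.011. MARS: 33 v 33, success 0.76 v 0.42, final boundary 2.055. Missing fraction: no expected rate is given, so the plan's 5 to 20% grid is used.

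**Plan's own power.** Simulating the three-look unpooled Z-test with the stated boundaries gives 0.910 for VENUS (stated 0.909) and 0.824 for MARS (stated 0.810). The inputs are read correctly.

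**Algebra with arm omitted.** Let d = p1 − p2, let m1 and m2 be the missing fractions (VOM-PV, PVAI), and let w1 and w2 be each arm's share of observed patients. Missing patients are filled at the pooled rate w1·p1 + w2·p2. Then

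- arm 1 becomes p1 − m1·w2·d;
- arm 2 becomes p2 + m2·w1·d;
- the difference becomes d × (1 − m1·w2 − m2·w1), which is d × (1 − m) when m1 = m2 = m.

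VENUS at 20% in both arms:

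- pooled rate = (180 × 0.56 + 156 × 0.38)/336 = 0.476;
- VOM-PV = 0.8 × 0.56 + 0.2 × 0.476 = 0.543;
- PVAI = 0.8 × 0.38 + 0.2 × 0.476 = 0.399;
- difference = 0.144 = 0.18 × 0.8.

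MARS: 0.34 × 0.9 = 0.306 at 10% and 0.34 × 0.8 = 0.272 at 20%.

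VENUS with unequal missingness:

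- 5% VOM-PV, 20% PVAI: observed 171 and 124.8, so w1 = 0.578 and w2 = 0.422. The factor is 1 − 0.05 × 0.422 − 0.20 × 0.578 = 0.863, giving 0.155.
- 20% VOM-PV, 5% PVAI: observed 144 and 148.2, so w1 = 0.493 and w2 = 0.507. The factor is 1 − 0.20 × 0.507 − 0.05 × 0.493 = 0.874, giving 0.157.

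The pull is toward zero whichever arm loses more.

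**Simulation.** Assumptions: four baseline covariates with log-odds 0.25, 0.25, 0.3 and 0.3 per SD; outcomes missing completely at random; 20 imputations with parameter draws; variance p(1−p)/n per arm; Rubin's rules for 0/1 draws; 3,000 to 6,000 replicates per cell. The rejection rows are for a single look at 180/156. They assume that MI is judged at 2.011, which the plan does not say.

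| VENUS, missing in both arms | 5% | 10% | 15% | 20% |
|---|---|---|---|---|
| Difference, algebra, no arm | 0.171 | 0.162 | 0.153 | 0.144 |
| Difference, simulated, no arm | 0.171 | 0.162 | 0.152 | 0.144 |
| Difference, simulated, with arm | 0.180 | 0.180 | 0.178 | 0.180 |
| Z beyond ±2.011: complete case | 0.89 | 0.87 | 0.86 | 0.83 |
| Z beyond ±2.011: draws, with arm | 0.89 | 0.87 | 0.86 | 0.83 |
| Z beyond ±2.011: draws, no arm | 0.87 | 0.82 | 0.77 | 0.70 |
| Z beyond ±2.011: P(y=1\|x) filled in, no arm | 0.88 | 0.85 | 0.81 | 0.77 |
| Complete case significant, MI not: draws, no arm | 2.1% | 5.6% | 10.4% | 16.0% |
| Same: filled in, no arm | 1.3% | 2.8% | 5.3% | 7.9% |
| Same: draws, with arm | 0.5% | 1.1% | 1.6% | 1.9% |

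At 20% missing, draws without arm also give too large a standard error: 0.059 against a true SD of 0.048. For MARS at 2.055, draws without v with arm reject in 0.70 v 0.78 at 10% and 0.55 v 0.72 at 20%. A second simulation with other assumed covariate effects (0.2, 0.1, 0.4, 0.5) gave VENUS differences without arm of 0.161 at 10% and 0.144 at 20%, so the shrinkage does not hinge on those values.

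**Under no effect** (VENUS, 0.47 in both arms, 20% missing), rejection at 2.011 is 0.048 for complete case, 0.049 for draws with arm, 0.018 for draws without arm, 0.027 for fill-in without arm and 0.079 for fill-in with arm. In the last case, at the planned 0.56 v 0.38, the plan's variance formula gives SE 0.054 against a true SD of 0.061. Adding arm without drawing outcomes therefore replaces one fault with another.

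**The case against.** The strongest reply is that the plan does not bind itself to this model. It commits to MI by Markov chain Monte Carlo, cites sources including a standard book on multiple imputation, and names Stata's MI routines. The covariate list is an example, and filling in one probability per patient sits poorly with MI at all. That stands, and it is why the point is conditional. But the example is the only specification given, and the general sentence mentions only covariate patterns. The choice about arm would otherwise be made with the data in hand.

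The MI is also secondary, and without arm it errs toward no difference, so it creates no false positive. That is correct and limits the seriousness.

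The missing rate is unknown and may be low: one week of monitoring suffices, and implanted devices may replace the external monitor. At 5% the effect is small, and the 20% column is the edge of the plan's grid, not a forecast.

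Finally, the rejection figures need a criterion that the plan does not state, and they describe a single final look. By the plan's Table 6, 0.033 + 0.547 = 0.580 of trials under the alternative cross a boundary before that look. Those figures are illustrative for this reason. The shrinkage of the estimate needs neither assumption.

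**Conclusion.** The concern holds as a conditional statement. If the described model is used, MI shrinks the treatment difference by the missing fraction when missingness is equal across arms, and by a similar amount when it is not. Over 5 to 20% missing, that is 0.9 to 3.6 percentage points of the 18-point VENUS difference; in MARS it is 3.4 points of 34 at 10% and 6.8 at 20%. The algebra rests on randomisation and on missingness unrelated to outcome within arm; the simulated figures add the covariate effects assumed above. The plan should be changed, but the fault does not threaten the primary analysis or its error rate. What is at risk is the credibility of a positive result when its named missing-data check is biased against it.

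**What to change.** In the Missing data paragraph, replace the example with a commitment that:

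- the imputation model includes randomised arm alongside age, gender, baseline AF duration and baseline LA volume, or imputation is done separately by arm;
- missing outcomes are imputed as 0/1 draws, not as P(y=1|x);
- estimates and variances are pooled by Rubin's rules.

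Arm as a covariate, with draws and Rubin's rules, was checked in both trials. In VENUS the simulated difference stays at 0.178 to 0.180. At the MARS size, with the four listed predictors plus arm and 20% missing, the mean difference is 0.335 against a true 0.34, and rejection under no effect (0.59 in both arms) is 0.054.

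The cost is one or two sentences in the SAP. The Stata routine is the same, no new data are needed, and the primary test does not change.

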Results. A group sequential trial with sample sizes of N1=180 and N2=156 at the final look achieves 91% power to detect a difference of 0.18 between a treatment group success proportion of 0.56 and a control group success proportion of 0.38 at the 0.05 significance level (alpha) using a two-sided Z-Test (Unpooled). The table below lists the sample sizes required for 91% power.

Table 5. Sample size requirements for a group sequential trial based on 100,000 iterations.

Value	95% LCL	95% UCL	Target	Actual	95% LCL	95% UCL	Beta		
0.909	0.908	0.911	0.050	0.049	0.048	0.051	0.091		
----- Average Sample Size -----									
-- Given H0 -- -- Given H1 --									
N1	N2	Grp1	Grp2	Grp1	Grp2	Diff0	Diff1	P1 H1	P2
180	156	179	155	144	125	0.00	0.18	0.56	0.38

Efficacy Monitoring. We propose to monitor efficacy at two interim time points and one final time period (i.e., three “looks”) when primary outcome data (12 month follow-up) are available for 1/3, 2/3 and 3/3 of the total sample size of VENUS subjects. For the VENUS trial, these values are provide in the following table in terms of *information time*:

Table 6. Efficacy monitoring schedule for VENUS with cumulative sample size, significance boundaries and 95%CIs, and alpha- and beta-spending.

Accumulated primary outcomes for VENUS						
Look	Accumulated Sample Size -----					
	Percent	VOM	PVAI	Total		
1	33.33	60	52	112		
2	66.67	120	104	224		
3	100.00	180	156	336		

Significance Boundaries with 95% Simulation Confidence Intervals						
Look	----- Z-Value Boundary -----			----- P-Value Boundary -----		
	Value	95% LCL	95% UCL	Value	95% LCL	95% UCL
1	+/- 3.953	3.809	4.289	0.000	0.000	0.000
2	+/- 2.543	2.516	2.578	0.011	0.010	0.012
3	+/- 2.011	1.994	2.036	0.044	0.042	0.046

Alpha-Spending						
Look	----- Target -----			----- Actual -----		
	--- Signif. Boundary---	Spending	Spending	Proportion	Cum.	
Z-Value	P-Value	Function	Function		H1 Sims	H1 Sims
Look	Scale	Scale	Alpha	Alpha	Cum. Alpha	Outside Signif. Boundary
1	+/- 3.953	0.000	0.000	0.000	0.000	0.033
2	+/- 2.543	0.011	0.012	0.011	0.012	0.547
3	+/- 2.011	0.044	0.038	0.038	0.049	0.329
						0.909
		Spent	Spent	Boundary		Cum. Boundary

The hypothesis test applied at the k th look is a two-tailed test of equality of two independent proportions, functionally composed as

$$Z_k = \frac{\hat{p}_{1k} - \hat{p}_{2k}}{\sqrt{\frac{\hat{p}_{1k}(1-\hat{p}_{1k})}{n_{1k}} + \frac{\hat{p}_{2k}(1-\hat{p}_{2k})}{n_{2k}}}}$$

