	95% LCL	95% UCL	Target	Actual	95% LCL	95% UCL			
0.810	0.807	0.812	0.050	0.049	0.047	0.050	0.190		
----- Average Sample Size -----									
-- Given H_0 -- -- Given H_1 --									
N1	N2	Grp1	Grp2	Grp1	Grp2	Diff0	Diff1	P1 H1	P2
33	33	33	33	28	28	0.00	0.34	0.76	0.42

Results. Group sequential trials with sample sizes of 33 and 33 at the final look achieve 81% power to detect a difference of 0.34 between a treatment group proportion of 0.76 and a control group proportion of 0.42 at the 0.05 significance level (alpha) using a two-sided Z-Test (Unpooled).

Efficacy Monitoring. We propose to monitor efficacy at two interim time points and one final time period (i.e., three “looks”) when primary outcome data (12-15 month follow-up) are available for 1/3, 2/3 and 3/3 of the total sample size of MARS subjects. For the MARS trial, these values are provide in the following table in terms of *information time*:

Table 10. Efficacy monitoring schedule for MARS with cumulative sample size, significance boundaries and 95%CIs, and alpha- and beta-spending.

Accumulated primary outcomes for MARS												
Look	Information Percent	Accumulated Sample Size			Z-Value Boundary			P-Value Boundary				
		Group 1	Group 2	Total	Value	95% LCL	95% UCL	Value	95% LCL	95% UCL		
1	33.33	11	11	22								
2	66.67	22	22	44								
3	100.00	33	33	66								
Significance Boundaries with 95% Simulation Confidence Intervals for Scenario 1												
----- Z-Value Boundary -----			----- P-Value Boundary -----									
Look	Value	95% LCL	95% UCL	Value	95% LCL	95% UCL	Value	95% LCL	95% UCL	Value	95% LCL	95% UCL
1	+/- 5.014	5.014	6.675	0.000	0.000	0.000						
2	+/- 2.708	2.640	2.708	0.007	0.007	0.008						
3	+/- 2.055	2.055	2.080	0.040	0.037	0.040						
Alpha-Spending												

Look	----- Target -----		----- Actual -----		Proportion		Cum.		H1 Sims		H1 Sims	
	-- Signif.	Boundary--	Spending	Spending	Cum.	Alpha	Cum.	Alpha	Outside	Signif.	Outside	Signif.
Z-Value	Scale	P-Value	Scale	Function	Alpha	Spent	Alpha	Spent	Boundary	Signif.	Boundary	Signif.
1	+/- 5.014	0.000	0.000	0.000	0.000	0.000	0.000	0.000	0.017	0.017	0.422	0.422
2	+/- 2.708	0.007	0.012	0.012	0.010	0.010	0.011	0.011	0.404	0.404	0.810	0.810
3	+/- 2.055	0.040	0.038	0.050	0.038	0.038	0.049	0.049	0.388	0.388		

[figure not shown]

Figure S2. Efficacy boundaries at 33%, 66%, and 100% accrual of MARS primary outcomes.

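### The six missing-data power tables do not follow their stated Z > 1.96 rule (1.645 reproduces them), and what they show is not power

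*Combined protocol and SAP*

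**What the plan says.** Section 6.0, Sensitivity analysis, imputes missing 12-month outcomes by binomial draws at the other arm's success rate. The draws are said to be "based on the success rate in the opposing arm, which enforces a high level of conservatism". The observed part of each arm enters as n0 × p, and the statistic is the unpooled Z. The plan then says "The power of the test is equal to the proportion of rejections among the" B iterations, with rejection defined as Z > 1.96. "The tables below present power as a function of VOM and PVAI success rates" and the missing proportion, for VENUS and MARS at each of three looks.

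Elsewhere in Section 6.0:

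- Efficacy Monitoring for VENUS says that the test at the kth "look is a two-tailed test of equality of two independent proportions".
- The VENUS design "achieves 91% power to detect a difference of 0.18 between a treatment group success proportion of 0.56" and a control proportion of 0.38. The MARS design is said to "achieve 81% power to detect a difference of 0.34 between a treatment group proportion of 0.76" and a control proportion of 0.42.
- Under Assumptions, "Patients who cannot be classified as successes or failures on the primary efficacy endpoint will be excluded from the primary analysis". Under Missing data, "MI will only be used for dealing with missing data as a secondary analysis tool of the primary endpoint".

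**The concern.** Two things look wrong, and they are independent.

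First, with nothing missing there is nothing to draw, so a cell must be 1 if Z exceeds 1.96 and 0 otherwise. Some cells with Z below 1.96 print 1.000.

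Second, at the design rates and full sample size the final-look tables print 1.000, where the design sections state 91% and 81%. Power cannot be both.

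These tables are the plan's only figures on what missing outcomes do to the primary result. A reader would conclude that 10% missing costs essentially nothing, even under an imputation described as conservative.

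**Working it through.** **Inputs.** Sample sizes (VOM/PVAI) are 60/52, 120/104 and 180/156 for VENUS, and 11/11, 22/22 and 33/33 for MARS. Planning rates are 0.56/0.38 and 0.76/0.42. Boundaries are 3.953/2.543/2.011 (Table 6) and 5.014/2.708/2.055 (Table 10). All come from Section 6.0.

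**1. Cells with nothing missing.** Z = (p1 − p2) / √[p1(1−p1)/n1 + p2(1−p2)/n2].

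- VENUS look 1, 0.56/0.38: 0.18 / √(0.2464/60 + 0.2356/52) = 0.18/0.0929 = 1.937. Printed 1.000.
- MARS look 1, 0.76/0.42: 0.34 / √(0.4260/11) = 0.34/0.1968 = 1.728. Printed 1.000.
- MARS look 2, 0.66/0.42: 0.24 / √(0.4680/22) = 0.24/0.1459 = 1.6455. Printed 1.000.
- MARS look 3, 0.71/0.52: 0.19 / √(0.4555/33) = 0.19/0.1175 = 1.617. Printed 0.000.

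Of the 150 such cells, 112 print 1.000 (smallest Z 1.6455) and 38 print 0.000 (largest Z 1.617). Twelve of the 112 have Z below 1.96. These rows alone place the cutoff between 1.617 and 1.646.

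**2. Cells with missing data.** Take VENUS look 3, 0.56/0.38, 20% missing, with 36 VOM and 31 PVAI outcomes missing.

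- Mean VOM rate: (144 × 0.56 + 36 × 0.38)/180 = 0.5240.
- Mean PVAI rate: (124.8 × 0.38 + 31 × 0.56)/156 = 0.4153.
- The difference is 0.1087 with standard error 0.0542, so Z is centred at 2.004.
- The draws give the difference a standard deviation of √(36 × 0.38 × 0.62/180² + 31 × 0.56 × 0.44/156²) = 0.0240, which is 0.442 in Z units.
- P(Z > 1.645) ≈ Φ(0.359/0.442) = 0.79. P(Z > 1.96) ≈ Φ(0.044/0.442) = 0.54.

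Exact enumeration gives 0.787 and 0.548. The plan prints 0.787.

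**3. All 750 cells by exact enumeration** (missing count rounded to the nearest whole number, observed part unrounded).

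- At 1.645, the largest difference from print is 0.006.
- At 1.96, 381 cells differ by more than 0.01 and 271 by more than 0.10. Print is higher in all 381.
- On a grid from 1.55 to 2.10 in steps of 0.0005, only 1.6445 and 1.6450 bring every cell within 0.01.

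Simulation noise cannot explain this: with 100,000 iterations the standard error is at most √(0.25/100,000) = 0.0016. The VENUS tables were partly scrambled in the extracted text and had to be reassembled. The 375 MARS cells needed no value dropped and give the same answer: none off by more than 0.01 at 1.645, and 213 off at 1.96.

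**4. Is it power?** Observed successes are fixed, so every cell with nothing missing is exactly 0 or 1. At the final look the planning-rate Z values are 3.355 and 2.992. Those cells therefore print 1.000 at 1.645, at 1.96 and at 2.011 or 2.055, so the cutoff does not explain the conflict with 91% and 81%.

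For actual power, both observed and missing outcomes were made binomial and the trial's boundaries applied cumulatively. With nothing missing this gives 0.910 for VENUS (plan 0.909) and 0.825 for MARS (plan 0.810). Raising each MARS boundary by 0.001 gives 0.811, so that gap comes from three-decimal boundaries on a discrete statistic.

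Final look, planning rates, by percentage missing:

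| | 0 | 5 | 10 | 15 | 20 |
|---|---|---|---|---|---|
| VENUS printed | 1.000 | 1.000 | 0.999 | 0.966 | 0.787 |
| VENUS at stated 1.96 | 1.000 | 1.000 | 0.984 | 0.849 | 0.548 |
| VENUS power, opposing-arm | 0.910 | 0.842 | 0.748 | 0.636 | 0.504 |
| VENUS power, complete-case | 0.910 | 0.895 | 0.877 | 0.860 | 0.840 |
| MARS printed | 1.000 | 1.000 | 1.000 | 0.896 | 0.517 |
| MARS at stated 1.96 | 1.000 | 1.000 | 0.914 | 0.495 | 0.298 |
| MARS power, opposing-arm | 0.825 | 0.719 | 0.654 | 0.515 | 0.375 |
| MARS power, complete-case | 0.825 | 0.805 | 0.786 | 0.739 | 0.729 |

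Read as power, cells with small differences err the other way. With nothing missing at the final look, VENUS 0.46/0.38 prints 0.000 against a power of 0.31, and MARS 0.71/0.52 prints 0.000 against 0.37. Over the 250 final-look cells, print is above opposing-arm power by more than 0.02 in 170 and below it by that much in 42.

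**The case against.** The plan prints its formula openly, with the observed part fixed, and cites a published imputation method. Conditioning on observed rates may be what was intended, in which case the second fault is only the word power, and relabelling cures it. That is fair for the label but leaves the cutoff untouched.

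The section does not claim to use the trial's boundaries, so setting its cells beside cumulative group-sequential power compares two different quantities. That also stands. The comparison shows what a reader who takes the tables as power would get wrong; it is not a breach of the stated rule.

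An opposing-arm figure below a complete-case figure is no error, because the scenario is meant to be adverse. So printed values of 0.787 and 0.517 at 20% missing, below complete-case power of 0.840 and 0.729, do not show that the tables are too low in their own scenario. There they are too high (0.504 and 0.375). The claim of error in both directions rests on the small-difference cells.

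Finally, no rule uses the tables, and neither the primary analysis nor the multiple imputation depends on them. That limits the consequence but does not make the figures right.

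**Conclusion.** Both faults hold. The tables contradict their own rejection rule, and every discrepancy above 0.01 makes the result look more robust than the rule allows. The clearest cases at the planning rates are the look-1 cells with nothing missing, printed 1.000 where the rule gives 0, and MARS at the final look with 15% missing, 0.896 against 0.495. The value 1.645 is inferred from the figures. It corresponds to a one-sided 5% test, which does not match the two-tailed design. Whatever the cutoff, the quantity is conditional on the observed rates and should not be called power.

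The opposing-arm power figures assume missing counts rounded to the nearest whole number. Rounding down or up as well gives MARS ranges of 0.72–0.77, 0.58–0.65, 0.51–0.58 and 0.37–0.44 at 5, 10, 15 and 20% missing; VENUS moves by less than 0.01. The complete-case figures assume that missingness is unrelated to outcome. This should be fixed, but it does not touch sample size, boundaries or the primary test.

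**What to change.** Preferred: rerun the simulation with observed outcomes also drawn as Binomial(n0, p), apply the trial's boundaries cumulatively, state how missing counts are rounded, and replace the six tables. Show complete-case power, which matches the planned primary analysis, beside the opposing-arm scenario, and label the latter as deliberately adverse.

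Minimum: keep the fixed-rate calculation, regenerate it so that the stated cutoff and the printed figures agree at a two-sided level, and retitle it as the chance that significance survives imputation given the observed rates. Add final-look results at the trial's own boundaries for 0/5/10/15/20% missing: VENUS at 2.011 gives 1.000/1.000/0.975/0.804/0.494, and MARS at 2.055 gives 1.000/1.000/0.914/0.432/0.237. At look 1 the corresponding planning-rate values are all 0 and tell the reader nothing.

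The cost is a short simulation and six replacement tables. The replacement power figures will be lower at the planning rates under the opposing-arm scenario and higher in small-difference cells. Nothing changes for patients or trial conduct.
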